1.0 Objectives

1.1 Study Objectives

Describe the purpose, specific aims or objectives. State the hypotheses to be tested.

The objective of this study is to evaluate the effectiveness of offering self-sampling for high-risk human papillomavirus (HPV) testing in increasing participation in cervical cancer screening.

Specifically, we will determine if women who are out-of-date for cervical cancer screening will be more likely to seek screening if offered the option to complete a self-sampled HPV test compared to standard of care. Eligible patients at Penn State Health St. Joseph (seen through Family and Community Medicine and through Women's Health) who are out-of-date with cervical cancer screening will be randomized to either a control arm or an intervention arm (2:1). Women in the control arm will receive a letter notifying them that they need to be screened and they should contact their primary care provider, according to standard clinical procedures (standard of care). Women in the experimental arm will receive (1) a slightly modified version of this letter informing them of a self-sampling option and (2) a pre-addressed post card to return to the study team if interested in self-sampling. Women who return the post card will then receive, via mail, a self-sampling kit to obtain a cervical sample for an HPV test.

For both arms, women whose cervical cancer screening test (collected by a provider or by the participant herself) indicate the presence of high-risk HPV will be directed to follow-up procedures following standard clinical practice.

Hypothesis: Women notified of a need for cervical cancer screening by letter who are offered self-sampling for cervical cancer screening will have a higher rate of screening that women notified by letter alone.

1.2 Primary Study Endpoints

State the primary endpoints to be measured in the study.

Clinical trials typically have a primary objective or endpoint. Additional objectives and endpoints are secondary. The endpoints (or outcomes), determined for each study subject, are the quantitative measurements required by the objectives. Measuring the selected endpoints is the goal of a trial (examples: response rate and survival).

The primary objective is to test the screening differences in control arm (i.e., receiving the standard reminder letter) versus the intervention arm (i.e., receiving a modified reminder letter plus postcard to request HPV self-sampling kit). The purpose is to assess the impact of mailing HPV home sampling kits to patients in need of cervical cancer screening on HPV screening rates.

The primary end point of 1) Completion of cervical cancer screening 2) Use of home cervical cancer screening kit will be evaluated over a three month time period after reminder letters are mailed.

1.3 Secondary Study Endpoints

State the secondary endpoints to be measured in the study.

The secondary endpoint is overall cervical cancer screening of people mailed a letter.

2.0 Background

2.1 Scientific Background and Gaps

Describe the scientific background and gaps in current knowledge.

For clinical research studies being conducted at Penn State Health/Penn State College of Medicine, and for other non-PSH locations as applicable, describe the treatment/procedure that is considered standard of care (i.e., indicate how patients would be treated in non-investigational setting); and if applicable, indicate if the treatment, drug, or device is available to patient without taking part in the study.

The American Cancer Society estimates that 4,170 women in the United States (US) will die from cervical cancer in 2018. It is possible to prevent many of these deaths through screening (e.g., with the human papillomavirus [HPV] test for cervical cancer) and appropriate follow-up in women with positive screens.¹

The U.S. Preventive Services Task Force (USPSTF) recommends that women ages 30-65 receive cervical cancer screening through (a) Pap testing every 3 years; (b) high-risk HPV testing every 5 years; or (c) Pap and high-risk HPV testing every 5 years². Other organizations, including the American College of Obstetrics and Gynecology and the American Cancer Society³, have different recommendations for the test modalities and intervals. Regardless of the specific measure of up-to-date with cervical cancer screening, rates of screening are suboptimal, and vulnerable subgroups (including women in rural areas, racial/ethnic minorities, women with low socioeconomic status, and women who are underinsured) are even less likely to be screened⁴. Most cases of cervical cancer are detected among women who are out-of-date for screening⁵.

An emerging area of evidence suggests that women can collect their own samples for high-risk HPV testing^{6,7}. Offering self-sampling for HPV testing to women who are out-of-date for screening has been associated with up to 9 times higher rates of screening than a normal reminder letter^{8,9,10}. This method of sample collection finds comparable clinical results as provider collection^{11,12}. In addition, this approach appears to be particularly effective among women who are out-of-date with screening¹³.

Based on this information, self-sampling for HPV testing may be a viable option for cervical cancer screening, particularly among women who do not obtain regular screening in a clinical setting. However, all previous studies have been conducted in a highly-controlled, well-resourced research context. We propose a study using real-world procedures that could pragmatically be adopted in primary care clinics, i.e., evaluating a reminder letter with a post card option to request an HPV self-sampling kit.

2.2 Previous Data

Describe any relevant preliminary data.

Previous studies on HPV self-sampling have found this approach to be appropriate for providing preventive care to underserved communities. One recent study concluded that mailing self-sampling kits to home addresses could be a more effective alternative to reminder letters.¹⁴ Other studies have demonstrated that HPV self-sampling tests are comparable to clinician-collected samples for HPV screening.¹⁵

The study team has been involved in many studies on cancer prevention and control and primary care relevant to this proposal. Cancer prevention studies performed by the study team include ongoing studies on acceptability and accuracy of self-sampling. These studies emphasize the urgent need for interventions to improve cervical cancer screening behaviors in vulnerable communities.

2.3 Study Rationale

Provide the scientific rationale for the research.

This pragmatic feasibility study will evaluate whether one method for offering self-sampling for HPV testing (i.e., with a post card to request a mailed kit) will increase cervical cancer screening rates.

3.0 Inclusion and Exclusion Criteria

Create a numbered list below in sections 3.1 and 3.2 of criteria subjects must meet to be eligible for study enrollment (e.g., age, gender, diagnosis, etc.).

Vulnerable Populations:

Indicate specifically whether you will include any of the following vulnerable populations in this research. You MAY NOT include members of these populations as subjects in your research unless you indicate this in your inclusion criteria because specific regulations apply to studies that involve vulnerable populations.

The checklists referenced below outline the determinations to be made by the IRB when reviewing research involving these populations. Review the checklists as these will help to inform your responses throughout the remainder of the protocol.

- **Children** –Review “HRP-416- Checklist - Children”
- **Pregnant Women** – Review “HRP-412- Checklist - Pregnant Women”
- **Cognitively Impaired Adults**- Review “HRP-417- Checklist - Cognitively Impaired Adults”
- **Prisoners**- Review “HRP-415- Checklist - Prisoners”
- **Neonates of uncertain viability or non-viable neonates**- Review “HRP-413- Checklist - Non-Viable Neonates” or “HRP-414- Checklist - Neonates of Uncertain Viability”

[Do not type here]

3.1 Inclusion Criteria

Create a numbered list of the inclusion criteria that define who will be included in your final study sample (e.g., age, gender, condition, etc.)

- Female patients at PSH St. Joe’s FCM residency clinic or women’s health clinic
- 30-65 years of age
- Out-of-date for cervical cancer screening
- Able to speak, read, and communicate well in English or Spanish
- Not greater than average risk for cervical cancer

3.2 Exclusion Criteria

Create a numbered list of the exclusion criteria that define who will be excluded in your study.

- Pregnant
- Incarcerated
- Greater than average risk for cervical cancer¹⁶
 - Already diagnosed with high-grade precancerous cervical cancer or cervical lesions
 - Have a compromised immune system
 - With in-utero exposure to diethylstilbestrol

- Unable to speak, read, and communicate well in English or Spanish
- Unable or unwilling to give implied consent or otherwise complete study requirements

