5.4.6 Debriefing

Explain whether and how subjects will be debriefed after participation in the study. If subjects will not be debriefed, provide a justification for not doing so. Add any debriefing materials to the study in CATS IRB.

Not applicable.

5.5 Informed consent will not be obtained – request to completely waive the informed consent requirement

Review “HRP-410-Checklist -Waiver or Alteration of Consent Process” to ensure that you have provided sufficient information.

5.5.1 Indicate why the research could not practicably be carried out without the waiver of consent

Currently, patients do not need to provide informed consent to receive reminders to obtain guideline-recommended clinical procedures. Requiring participants to provide consent would critically reduce the sample size. More importantly, requiring potential participants to consent to receive information about cervical cancer screening could give them the impression that screening is somehow “new” or “experimental,” which could lead to patients who are out-of-date with cervical cancer screening to avoid scheduling a screening.

5.5.2 Describe why the research involves no more than minimal risk to subjects.

Participants will receive a letter directing them to receive a guideline-recommended procedure that is considered standard of care. These procedures do not post more than minimal risks to subjects.

5.5.3 Describe why the alteration/omission will not adversely affect the rights and welfare of subjects.

The rights and welfare of subjects will be maintained because they will still have the option of determining whether or not they want to schedule a cervical cancer screening.

5.5.4 If the research involves using identifiable private information or identifiable biospecimens, describe why the research could not be practicably be carried out without using such information or biospecimens in an identifiable format.

Our outcomes analysis will assess (1) participation in cervical cancer screening during the follow-up period (yes or no), and (2) whether any follow-up procedures were indicated for that patient. The follow up period will consist of three months after the mailing. We will assess differences in these outcomes for participants who receive the standard of care letter versus a modified letter with an option for HPV self-sampling. If we did not use identifiable health information, we would not be able to link the letter type to clinical outcomes.

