6.2.1.2 Plan to destroy identifiers or a justification for retaining identifiers

Describe the plan to destroy the identifiers at the earliest opportunity consistent with the conduct of the research. Include when and how identifiers will be destroyed. If identifiers will be retained, provide the legal, health or research justification for retaining the identifiers.

Identifying information will be destroyed after data collection and cleaning is complete.

6.2.2 Explanation for why the research could not practicably be conducted without access to and use of PHI

Provide an explanation for why the research could not practicably be conducted without access to and use of PHI.

Access to PHI is required to identify women who are within the specified age range (30-65 years); out of date with cervical cancer screening; and don't have any of the disqualifying conditions.

Participants who request and return a self-sampling kit are providing their implied consent to collect their research information. Participants who do not request the self-sampling kit are receiving standard

6.2.3 Explanation for why the research could not practicably be conducted without the waiver or alteration of authorization

Provide an explanation for why the research could not practicably be conducted without the waiver or alteration of authorization.

Obtaining informed consent from all participants before accessing their PHI to determine screening status would be infeasible due to the large number of patients who meet inclusion criteria. Receiving a reminder letter about cervical cancer screening is also standard of care for those who are out-of-date, so there would be no reason to consent these patients prior to sending the letter.

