8.0 Subject Numbers and Statistical Plan

8.1 Number of Subjects

Indicate the maximum number of subjects to be accrued/enrolled. Distinguish between the number of subjects who are expected to be enrolled and screened, and the number of subjects needed to complete the research procedures if applicable (i.e., numbers of subjects excluding screen failures.)

The study seeks to have 1,211 participants. There will be 807 participants randomized into the control arm and 404 into the intervention arm.

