8.2 Sample size determination

If applicable, provide a justification of the sample size outlined in section 8.1 to include reflections on, or calculations of, the power of the study.

We assume a 15% response rate from the control group, i.e., in response to a standard reminder letter, for a final $n=122$.¹⁷ We further assume a 30% response rate for the intervention group, i.e., requesting an HPV self-sampling¹⁸ kit, for a final $n=122$ for this group. In total, we expect at least 244 participants to respond to their reminders to receive cervical cancer screening.

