8.3 Statistical methods

Describe the statistical methods (or non-statistical methods of analysis) that will be employed.

We will calculate the proportion of participants who obtain cervical cancer screening (in the Penn State Health St. Joseph's FCM or Women's Health clinics or with self-collected samples for HPV testing) by arm within three months of the initial mailing. We will use chi-squared tests to compare these proportions, using an alpha of .05 and a beta of 0.80.

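### Section 8.2 treats the expected responders (122 per arm) as the final sample, so the size of 1,211 and the 2:1 ratio are not justified for the comparison of 807 with 404 women in 8.3

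*Combined protocol and SAP*

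**What the plan says.** All references are to the combined protocol and SAP.

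- **8.2, sample size.** "We assume a 15% response rate from the control group, i.e., in response to a standard reminder letter, for a final $n=122". The intervention arm gets a 30% rate, described as requesting a kit, and again a final n of 122. The section closes: "In total, we expect at least 244 participants to respond to their reminders to receive cervical cancer screening".
- **8.1, number of subjects.** "There will be 807 participants randomized into the control arm and 404 into the intervention arm", 1,211 in total. Section 4.2.3 repeats the numbers and the 2:1 ratio.
- **8.3, statistical methods.** The outcome is the proportion of participants screened, in clinic or by self-collected sample, by arm within three months of mailing. "We will use chi-squared tests to compare these proportions, using an alpha of .05 and a beta of 0.80".
- **Who is kept.** 7.2.1 randomises from the EHR list before anything is mailed. 3.3.1 foresees no removal by the investigators, and 3.3.2 keeps the data of women who withdraw up to withdrawal. 5.5.4 compares outcomes "for participants who receive the standard of care letter versus a modified letter with an option for HPV self-sampling". For the secondary endpoint, 1.3 says: "The secondary endpoint is overall cervical cancer screening of people mailed a letter".
- **Consent.** 3.2 excludes women who are "Unable or unwilling to give implied consent or otherwise complete study requirements". 5.3.1 places implied consent at the return of the postcard, and 6.2.2 says: "Participants who request and return a self-sampling kit are providing their implied consent to collect their research information". Section 5.5 argues for a complete waiver.

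No section names the analysis population.

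**The concern.** A responder count is the numerator of the outcome proportion. Calling it the final n makes it a denominator. If a sample-size calculation is done for the outcome rates and then inflated by those same rates, the result answers no question that the trial asks. The total of 1,211 and the control-heavy ratio would then rest on equalising responder counts, and the reader would not know what difference the 807 vs 404 comparison can detect.

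A second difficulty lies in the same sentences. The 30% describes women who ask for a kit. A woman who asks for one may never return it, and a woman who does not ask may be screened in clinic. The plan gives no figure for completed screening in the intervention arm, although that is what 8.3 tests.

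**Working it through.** **Inputs.** Rates of 15% and 30% (8.2); alpha 0.05 and chi-squared test (8.3); 807 and 404 (8.1). Two assumptions are mine: the test is two-sided, and the beta of 0.80 in 8.3 means power of 0.80.

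**Step 1: reproduce the plan's figures.** For two equal groups, pooled variance under the null and no continuity correction:

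n = [1.960·√(2·0.225·0.775) + 0.8416·√(0.15·0.85 + 0.30·0.70)]² / 0.15² = (1.1575 + 0.4889)² / 0.0225 = 120.47, so 121 per arm.

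Divide each arm by its own response rate:

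- control: 121 / 0.15 = 806.67, so 807
- intervention: 121 / 0.30 = 403.33, so 404
- total: 1,211

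This is 8.1 exactly. Going back, 807 × 0.15 = 121.05 and 404 × 0.30 = 121.2; each rounds up to the 122 in 8.2. The 2:1 ratio is 0.30 / 0.15. One-sided (95), continuity-corrected (134), 90% power (161), unpooled (118), arcsine (119) and 2:1 (175 and 88) versions do not lead to 807 and 404 after the same division.

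**Step 2: size needed if the rates are used once.** At 2:1 the pooled proportion is (2·0.15 + 0.30)/3 = 0.20, and the intervention arm needs

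[1.960·√(0.20·0.80·1.5) + 0.8416·√(0.15·0.85/2 + 0.30·0.70)]² / 0.15² = 87.18, so 88, with 176 controls: 264 women. 1,211 / 264 = 4.6.

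**Step 3: power of 807 vs 404.** Power = Φ[(|p2 − 0.15| − 1.960·s0) / s1]. Here s0 is the standard error of the difference with the pooled proportion and s1 that with separate proportions.

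| Intervention proportion screened (control 15%) | s0 | s1 | Power |
|---|---|---|---|
| 30% (the rate in 8.2) | 0.02438 | 0.02603 | above 99.9% |
| 25% (assumed) | 0.02358 | 0.02494 | 98.4% |
| 21.5% | 0.02298 | 0.02399 | 79.7% |
| 20% (assumed) | 0.02271 | 0.02354 | 59% |
| 18% (assumed) | 0.02234 | 0.02288 | 27% |

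For example, at 30%: (0.15 − 0.04778)/0.02603 = 3.93, so power is 0.99996. Exact binomial enumeration of the uncorrected chi-squared test agrees: 0.99997 at 30%, 0.986 at 25%, 0.798 at 21.5%, 0.590 at 20% and 0.272 at 18%.

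**Step 4: effect of the ratio.** The same total split 1:1 would have 83.4% power at 15% vs 21.5%, against 79.7% at 2:1. The loss is modest, but the plan gives no reason for accepting it.

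**The case against.** The strongest reply is that final n is loose wording for expected responders. Section 8.2 never says that only responders are analysed, and its last sentence treats them as a subset of the participants. Sections 3.3.1, 3.3.2, 5.5.4 and 7.2.1 all point to keeping everyone randomised. This stands as a reading of the analysis. It does not rescue the justification: once all 1,211 women are the denominator, the calculation that yields 807 and 404 no longer applies.

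It can also be said that the division is nowhere printed, and that the printed 122 would give 814 and 407. Both are true, so the derivation must be called an inference. An exact match on both arms and on the total makes coincidence implausible.

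Finally, the trial is larger than 15% vs 30% requires, so on the stated rates there is no shortage of power. That also stands, but the comfort depends on 30% being screened, and 30% is the assumed rate of requests.

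A reader might infer more: that the exclusion in 3.2 removes non-responders from the intervention arm after randomisation, or that the trial will compare 122 with 122 responders and so cannot test its hypothesis. The documents do not support either. Eligibility is applied by EHR query before mailing (4.2.4, 7.2.1), a waiver is argued for in 5.5, and no section plans a responders-only analysis.

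**Conclusion.** The size and power justification is wrong as written. By inference, the response rates were used both as the effect to detect and as attrition before analysis. On the rates in 8.2, 807 vs 404 gives power above 99.9% rather than 80%, and is about 4.6 times the 264 women needed at 2:1. The difference detectable with 80% power is 15% vs about 21.5%, and the plan does not state it. Whether the trial is amply powered or underpowered depends on completed screening in the intervention arm, for which there is no assumption: power is about 98% to 99%, 59% or 27% if 25%, 20% or 18% are screened. These three rates are illustrations, not figures from the plan.

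The result rests on a 15% control rate, a two-sided test, beta of 0.80 meaning power, and analysis of everyone randomised. No bias in the planned comparison is shown. The consent bullet in 3.2 is a wording inconsistency of second rank: as 5.3.1 and 6.2.2 describe it, implied consent is an act open only to the intervention arm after randomisation, so it cannot serve as an entry criterion for both arms.

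**What to change.** - **8.3:** state that every randomised woman is analysed in her assigned arm, with planned denominators of 807 and 404. Replace the beta of 0.80 with a power of 0.80 and give the sidedness.
- **8.2:** call 122 and 122 the expected responders. Replace the kit-request rate with an assumed proportion completing screening within three months among all women mailed, and give its source. State the power or the detectable difference for 807 vs 404. The total of 1,211 may stay if it is justified on that basis.
- **Allocation:** give a reason for 2:1 that does not rely on equal responder counts, or reconsider it.
- **3.2:** limit the implied-consent bullet to kit mailing and testing, so that it agrees with the waiver argued in 5.5.

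The cost is wording and one recalculation. No additional women or data are needed if 1,211 is kept.

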3.3 Early Withdrawal of Subjects

3.3.1 Criteria for removal from study

Insert subject withdrawal criteria (e.g., safety reasons, failure of subject to adhere to protocol requirements, subject consent withdrawal, disease progression, etc.).

There are no foreseeable reasons why a study subject might be removed by the investigators from the study. Subjects can voluntarily withdraw from the study at any time and for any reason.

3.3.2 Follow-up for withdrawn subjects

Describe when and how to withdraw subjects from the study; the type and timing of the data to be collected for withdrawal of subjects; whether and how subjects are to be replaced; the follow-up for subjects withdrawn from investigational treatment.

The withdrawal will be documented. Subjects who withdraw will be asked to describe why they are withdrawing so that we may better understand the study population. Withdrawn subjects will not be replaced but all data collected up until the point of withdraw will be included in data analysis.

